2.5.5 Unscheduled visits

Unscheduled visit measurements will be used for computation of baseline and PCSAs. All visits will be re-allocated, and re-allocated visits measurements will be included in the by-visit summaries.

2.5.6 Pooling of centers for statistical analyses

Not applicable.

2.5.7 Statistical technical issues

Not applicable.

3 INTERIM ANALYSIS

No formal interim analysis is planned.

4 DATABASE LOCK

The database is planned to be locked approximately at 4 weeks after last patient last visit.

5 SOFTWARE DOCUMENTATION

The population PK analysis will be performed using the non-linear mixed effect modeling approach as implemented in the Monolix (v.2019R2 or later, Lixoft) software. Data manipulation, additional calculations and graphics will be performed using R (v. 3.5 or later), The R Foundation for Statistical Computing)"

All other summaries and statistical analyses will be generated using SAS version 9.4 or higher.

6 REFERENCES

1. REFBIB000665
2. REFBIB000765
3. REFBIB000865
4. REFBIB000965
5. REFBIB001065

7 LIST OF APPENDICES

Appendix A Flow chart

Appendix B Potentially clinically significant abnormality criteria

Appendix BC References

Appendix A Flow chart

Procedure	Screening (up to 1 day before Day 0)	Treatment Period and post-treatment surveillance (Days)												Follow-up (Days)								Notes	
		0a						1	2	3	4	5	6	7	10	14 ±1	21 ±2	28 ±2					
		Hours post-dose																					
		0	1	2	4	6	8	12	18	24	30	36	48	72	96	120	144	168					
Visit	1b																		10	11	12	13c	
Informed consent	X																						
Demography, medical history	X																						
Inclusion/ exclusion criteria	X																						
IRTcall	X	X																				X	
Randomization		X																					
Hospitalization		←-----→.....→																					All patients hospitalized for 48 h post dosing or up to 4 days in case malaria symptoms and/or parasitemia persist at the end of day 2 or longer upon investigator's judgment
Treatment																							
FQ			X																				Dosing in fasted condition (see Section 6.3.1 of protocol)
OZ439			X																				
Rescue therapy ^d				←	X	
Prior and concomitant medication	X	X								X			X	X	X	X	X	X	X	X	X	X	
Activity																							
Physical exam & malaria signs & symptoms	X									X			X	X	(X)	(X)			X			X	Physical exam to be performed at discharge from the hospital
Height	X																						

Procedure	Screening (up to 1 day before Day 0)	Treatment Period and post-treatment surveillance (Days)												Follow-up (Days)								Notes		
		0a						1	2	3	4	5	6	7	10	14 ±1	21 ±2	28 ±2						
		Hours post-dose																						
		0	1	2	4	6	8	12	18	24	30	36	48	72	96	120	144	168						
Visit	1b	2						3			4	5	6	7	8	9	10	11	12	13c				
Weight	X												(X)	(X)	(X)						X	Weight to be taken at discharge from hospital		
Temperature (single)e	X		X	X		X		X	X	X	X	X	X	X	X	X	X	X	X	X		Measurement required within 4 hours prior to dosing		
Asexual & sexual parasite count (thick & thin blood films)e	X				X		X	X	X	X	X	X	X	X	X	X	X	X	X	X	X			
qPCR, parasite genotyping, RT-qPCR gametocyte detection samplingf	X					X		X	X	X	X	X	X	X	X	X	X	X	X	X	X			
Safety																								
12-Lead ECGg	X	X		X	X	X	X		X			X	(X)	(X)			X					72 and 96 h post-dose if participant still hospitalized		
Vital signs	X				X		X		X			X	(X)	(X)		X	X	X	X	X	X	Vital signs to be taken at discharge from the hospital		
AEs	<=====→																							
Laboratory testing																								
Clinical laboratory safetyh	X												X	(X)	(X)			X	X	X		72 and 96 h post-dose if participant still hospitalized		
Viral hepatitis serology	X																					rapid spot test (HAV IgM, HBsAg, HCV Ab), and/or HCV RNA (if known)		
Pregnancy test	X																				X	Urine beta-HCG is the minimum acceptable test. Result must be confirmed negative prior to dosing.		
PK OZ439i		X	X	X	X	X		X		X			X	X		X		X				Not measured in Arm A; Plasma samples		

Procedure	Screening (up to 1 day before Day 0)	Treatment Period and post-treatment surveillance (Days)												Follow-up (Days)								Notes			
		0a				1	2	3	4	5	6	7	10	14 ±1	21 ±2	28 ±2									
		Hours post-dose																							
		0	1	2	4	6	8	12	18	24	30	36	48	72	96	120	144	168							
Visit	1b	2				3			4	5	6	7	8	9	10	11	12	13c							
PK FQ (+metabolite)/		X	X		X	X	X	X		X			X			X		X		X		X			

- a Day 0 is defined as the day of single dose treatment to comply with WHO guidelines (5).
- b Visit 1 may occur on the same day as Visit 2 provided that all baseline assessments and biology results (including parasitemia and laboratory safety) are obtained before patient randomization.
- c In case of study discontinuation, all assessments planned on Day 28, including rescue therapy administration, should be performed as far as possible.
- d Administered at Day 28 for participants who reach Day 28 without having received a rescue medication. At each contact post-dosing, conditions for treatment failure will be assessed and rescue therapy will be given accordingly. See details in [Section 7.7.1](#) of protocol
- e Local thick and thin blood films performed at the site, before Informed Consent signature, according to local standard procedures and within 4 hours prior to dosing, can be used as screening/ pre-dose parasitemia assessments ([Section 9.1.1.1](#) of protocol) provided that a standard procedure is in place at site and blood films staining is performed according to the study operational manual. Blood films (thick and thin) and temperature measurements need to be confirmed as follows: when 1st parasite clearance and 1st temperature < 37.5 °C, measurements need to be confirmed with second reading 6 to 12 hours after the first measurement (ie, to determine Parasite Clearance and Fever Clearance). The first measurement (if confirmed) will be considered the 'Clearance Time'. Asexual and sexual counts will be measured separately: only asexual count will be used as parasitemia for evaluation of study endpoints. If parasites have not cleared within 72 hours after IMP administration and criteria for rescue medication are not met at 72 hours post-dose, blood films should continue to be taken according to site standard practice (or at minimum every 8 hours) until parasite clearance is shown or until criteria for rescue medication are met (see [Section 7.7.1](#) of protocol). If these additional blood smears are taken they should be recorded as unscheduled visits in the e-CRF. Axillary temperature should be recorded, if the axillary method is not possible, an alternative route (oral, tympanic, rectal) may be used. Within an individual participant the same method of temperature measure should be used throughout the study.
- f RT-qPCR and qPCR will be performed at all parasitemia time-points (To be collected, according to the schedule and the instructions reported in the study operational manual). Parasite genotyping analysis will be performed on previously collected blood spot sample only in case of a positive blood film after initial parasite clearance: one pre-dose sample and one sample at 18 or 24 hours post dosing. A further sample will be analyzed at the time point at which recrudescence/re-infection occurs (if applicable).
- g Single local ECG reading for inclusion purpose and triplicate central ECG reading for safety evaluation during study.
- h Laboratory safety will be performed locally: hematology, clinical chemistry, and urinalysis (see [Appendix 2](#) of protocol for details).
- i Where time points coincide, the PK samples should be taken after measurement of vital signs, temperature, and ECG. A PK sample (OZ439 and FQ) should be obtained if possible when QTcF >500 ms or QTcF is prolonged by >60 ms from baseline, or when increased ALT is measured (see [Section 9.2](#) of protocol). PK samples numbering is detailed in Table 3 of protocol.

AE: adverse event; e-CRF: electronic case report form; ECG: electrocardiogram; FQ: ferroquine; HAV IgM: hepatitis A immunoglobulin M; HBsAg: hepatitis B surface antigen; HCG: human chorionic gonadotropin; HCV Ab: hepatitis C virus antibody; HCV RNA: hepatitis C virus ribonucleic acid; IMP: investigational medicinal product; IRT: Interactive response technology; PK: pharmacokinetics; qPCR: quantitative polymerase chain reaction; RT-qPCR: quantitative reverse transcription polymerase chain reaction; WHO: World Health Organization

Appendix B Potentially clinically significant abnormality criteria

Laboratory parameter	Adults	Children
PCSA criteria n/N1 (%)		
Haemoglobin		
Low	≤ 115 g/L (Male) ≤ 95 g/L (Female)	28 days/1 month to 23 months old : < 90 g/L 24 months/2 years to <16/18 years old : < 100 g/L
Decrease from baseline	≥20 g/L	≥ 20 g/L
High (adults)	≥ 185 g/L (Male) ≥ 165 g/L (Female)	
Hematocrit		
Low	≤ 0.37 v/v (Male) ≤ 0.32 v/v (Female)	28 days/1 month to 23 months old: < 0.29 v/v 24 months/2 years to <16/18 years old: < 0.32 v/v
High	≥ 0.55 v/v (Male) ≥ 0.5 v/v (Female)	28 days/1 month to 23 months old: > 0.42 v/v 24 months/2 years to <16/18 years old: > 0.47 v/v
Erythrocyte Count		
High (adults)	≥ 6 Tera/L	
Platelet Count		
Low	< 100 Giga/L	< 100 Giga/L
High	≥ 700 Giga/L	> 700 Giga/L
Leukocytes		
Low	< 3.0 Giga/L (Non-Black); < 2.0 Giga/L (Black)	Birth/0 to 23 months old : <4.0 Giga /L 24 months/2 years to <6 years old: <3.0 Giga /L 6 to <12 years old : <5.0 Giga /L 12 to 16/18 years old : <4,5 Giga /L Birth/0 to 27 days old : >25.0 Giga /L
High	≥ 16.0 Giga/L	28 days/1 month to 23 months old: >20.0 Giga /L 24 months/2 years to <6 years old: >16.0 Giga /L 6 to <12 years old : >17.0 Giga /L 12 to 16/18 years old : >13.5 Giga /L
Neutrophils		

Laboratory parameter	Adults	Children
PCSA criteria n/N1 (%)		
Low	< 1.5 Giga/L (Non-Black); < 1.0 Giga/L (Black)	Birth/0 to 27 days old : <4 Giga /L (1 day old) <1.5 Giga /L (2-7 days old) <1.25 Giga /L (>7 day-1 month old) 28 days/1 month to 23 months old: <1.0 Giga /L (1-3 months) <1.2 Giga /L (3-24 months) 24 months/2 years to <16/18 years old: <1.2 Giga /L >1 ULN
High (children)		
Lymphocytes		
Low (children)		Birth/0 to 27 days old : <1.2 Giga /L 28 days/1 month to 23 months old: <2.0 Giga /L 24 months/2 years to <12 years old: <1.0 Giga /L 12 to 16/18 years old : <0.6 Giga /L
High	> 4.0 Giga/L	Birth/0 to 27 days old : >17.0 Giga /L 28 days/1 month to 23 months old: >13.5 Giga /L 24 months/2 years to <6 years old: >9.5 Giga /L 6 to <12 years old : >8.0 Giga /L 12 to 16/18 years old : >6 Giga /L
Monocytes		
High (adults)	> 0.7 Giga/L	
Basophils		
High (adults)	> 0.1 Giga/L	
Eosinophils		
High	> 0.5 Giga/L or > ULN (if ULN ≥ 0.5 Giga/L)	> 0.5 Giga/L or > ULN (if ULN > 0.5 Giga/L)
Glucose		
Low	≤ 3.9 mmol/L and < LLN	<2.7 mmol/L

Laboratory parameter	Adults	Children
PCSA criteria n/N1 (%)		
High	≥11.1 mmol/L (unfasted); ≥ 7 mmol/L (fasted)	≥10.0 mmol/L (unfasted) ≥7 mmol/L (fasted after >12 hours of fast)
Albumin		
Low (adults)	≤ 25 g/L	
Creatine Kinase		
High, all grades	> 3 ULN	≥ 3 ULN
At least grade 1 (adults)	> 3 ULN	
At least grade 2 (adults)	> 10 ULN	
Sodium		
Low	≤ 129 mmol/L	≤129 mmol/L
High	≥ 160 mmol/L	≥150 mmol/L
Potassium		
Low	< 3 mmol/L	Birth/0 to 27 days old : ≤3.0 mmol/L 28 days/1 month to 16/18 years old : ≤3.5 mmol/L
High	≥ 5.5 mmol/L	Birth/0 to 27 days old : ≥7.0 mmol/L 28 days/1 month to 23 months old : ≥6.0 mmol/L 24 months/2 years to 16/18 years old : ≥5.5 mmol/L
Creatinine		
High	≥ 150 µmol/L	Birth/0 to <6 years old : >53 µmol/L 6 years to <12 years old: >90 µmol/L 12 years to 16/18 years old: >132 µmol/L
Increase from baseline		
At least grade 1 (adults)	≥ 30% change from baseline	
At least grade 2 (adults)	≥ 100% change from baseline	
Creatinine Clearance		

Laboratory parameter	Adults	Children
PCSA criteria n/N1 (%)		
Low, all grades	< 90 mL/min*	Birth/0 to 27 days old : < 25 mL/min/1.73m ² ** 28 days/1 month to 23 months old: < 45 mL/min/1.73m ² ** From 2 years old : < 60 mL/min/1.73m ² **
Mild (adults)	[60 – 90[mL/min*	
Moderate (adults)	[30 – 60[mL/min*	
Severe (adults)	[15 – 30[mL/min*	
End stage (adults)	< 15 mL/min*	
*MDRD or Cockcroft-Gault equation		
**GFR Bedside Schwartz Formula Based on normal ranges: 20 to 50 (<8 days), 25 to 80 (8 days to 1 month), 30 to 90 (1-6 months), 40 to 115 (6-12 months), 60 to 190 (12-23 months), 90 to 165 (2-12 years), 80-120 (After 12 years)		
BUN		
High	≥ 17 mmol/L	Birth/0 to 27 days old : ≥ 4.3 mmol/L 28 days/1 month to 16/18 years old: ≥ 6.4 mmol/L
Alanine Aminotransferase		
High, at least grade 1	> 3 ULN	≥ 3 ULN
High, at least grade 2	> 5 ULN	≥ 5 ULN
High, at least grade 3	> 10 ULN	≥ 10 ULN
High, at least grade 4	> 20 ULN	≥ 20 ULN
Aspartate Aminotransferase		
High, at least grade 1	> 3 ULN	≥ 3 ULN
High, at least grade 2	> 5 ULN	≥ 5 ULN
High, at least grade 3	> 10 ULN	≥ 10 ULN
High, at least grade 4	> 20 ULN	≥ 20 ULN
Alkaline phosphatase		
High	> 1.5 ULN	≥ 1.5 ULN
Total Bilirubin		
High, all grades	> 1.5 ULN	≥ 1.3 ULN
At least grade 1 (adults)	> 1.5 ULN	

Laboratory parameter	Adults	Children
PCSA criteria n/N1 (%)		
At least grade 2 (adults)	> 2 ULN	
Alanine Aminotransferase and tot bilirubin		
High	ALT > 3 ULN and TBILI > 2 ULN	ALT \geq 3 ULN and TBILI \geq 2 ULN
Direct bilirubin and total bilirubin		
High	BILDIR >35% TBILI and TBILI >1.5 ULN	BILDIR >35% TBILI and TBILI \geq 1.3 ULN

References:

- for adults: Criteria for Potentially Significant Abnormalities – for Phase 2/3 studies (oncology excepted) - Version 3.0 - 21-MAY-2014
- for children: Criteria for Potentially Clinically Significant Abnormalities for Studies in Children - Version 3.0 - 21-MAY-2014

ECG Parameter	Adults	Children
PCSA criteria n/N1 (%)		
Heart rate		
Low, at least grade 1 (adults)	<50 bpm	
Low, at least grade 2 (adults)	<40 bpm	
Low, at least grade 3 (adults)	<30 bpm	
Low and decrease from baseline, all grades	<50 bpm and decrease from baseline \geq 20 bpm	Birth/0 to 27 days old : \leq 90 bpm and decrease from baseline \geq 20 bpm 28 days/1 month to 23 months old: \leq 80 bpm and decrease from baseline \geq 20 bpm 24 months/2 years to <6 years old: \leq 75 bpm and decrease from baseline \geq 20 bpm 6 to <12 years old : \leq 50 bpm and decrease from baseline \geq 20 bpm 12 to 16/18 years old : \leq 50 bpm and decrease from baseline \geq 20 bpm
At least grade 1 (adults)	<50 bpm and decrease from baseline \geq 20 bpm	
At least grade 2 (adults)	<40 bpm and decrease from baseline \geq 20 bpm	
At least grade 3 (adults)	<30 bpm and decrease from baseline \geq 20 bpm	
High, at least grade 1 (adults)	>90 bpm	
High, at least grade 2 (adults)	>100 bpm	
High, at least grade 3 (adults)	>120 bpm	
High and increase from baseline, all grades	>90 bpm and increase from baseline \geq 20bpm	Birth/0 to 27 days old : \geq 190 bpm and increase from baseline \geq 20 bpm 28 days/1 month to 23 months old: \geq 175 bpm and increase from baseline \geq 20 bpm 24 months/2 years to <6 years old: \geq 140 bpm and increase from baseline \geq 20 bpm 6 to <12 years old : \geq 120 bpm and increase from baseline \geq 20 bpm 12 to 16/18 years old : \geq 120 bpm and increase from baseline \geq 20 bpm
At least grade 1 (adults)	>90 bpm and increase from baseline \geq 20bpm	
At least grade 2 (adults)	>100 bpm and increase from baseline \geq 20bpm	
At least grade 3 (adults)	>120 bpm and increase from baseline \geq 20bpm	

PR

ECG Parameter	Adults	Children
PCSA criteria n/N1 (%)		
High, all grades	>200 ms	Birth/0 to 27 days old : \geq 120 ms 28 days/1 month to 23 months old: \geq 140 ms 24 months/2 years to <6 years old: \geq 160 ms 6 to <12 years old : \geq 170 ms 12 to 16/18 years old : \geq 180 ms
At least grade 1 (adults)	>200 ms	
At least grade 2 (adults)	>220 ms	
At least grade 3 (adults)	>240 ms	
High and increase from baseline (adults)		
At least grade 1	>200 ms and increase from baseline \geq 25%	
At least grade 2	>220 ms and increase from baseline \geq 25%	
At least grade 3	>240 ms and increase from baseline \geq 25%	
QRS		
High, all grades	>110 ms	Birth/0 to 27 days old : \geq 85 ms 28 days/1 month to 23 months old: \geq 85 ms 24 months/2 years to <6 years old: \geq 95 ms 6 to <12 years old : \geq 100 ms 12 to 16/18 years old : \geq 110 ms
At least grade 1 (adults)	>110 ms	
At least grade 2 (adults)	>120 ms	
High and increase from baseline (adults)		
At least grade 1	>110 ms and increase from baseline \geq 25%	
At least grade 2	>120 ms and increase from baseline \geq 25%	
QTc Fridericia		
Increase from baseline, Grade 1	Increase from baseline]30-60] ms	All age classes: Increase from baseline (30-60] ms

ECG Parameter	Adults	Children
PCSA criteria n/N1 (%)		
Increase from baseline, Grade 2	Increase from baseline >60 ms	All age classes: Increase from baseline >60 ms

References:

- for adults: Criteria for Potentially Significant Abnormalities – for Phase 2/3 studies (oncology excepted) - Version 3.0 - 21-MAY-2014
- for children: Criteria for Potentially Clinically Significant Abnormalities for Studies in Children - Version 3.0 - 21-MAY-2014

Vital signs parameter	Adults	Children
PCSA criteria n/N1 (%)		
Systolic blood pressure supine		
Low and decrease from baseline	≤ 95 mmHg and decrease from baseline ≥ 20 mmHg	Birth/0 to 27 days old : ≤ 60 mmHg and decrease from baseline ≥ 20 mmHg 28 days/1 month to 23 months old: ≤ 70 mmHg and decrease from baseline ≥ 20 mmHg 24 months/2 years to <6 years old: ≤ 70 mmHg and decrease from baseline ≥ 20 mmHg 6 to <12 years old : ≤ 80 mmHg and decrease from baseline ≥ 20 mmHg 12 to 16/18 years old : ≤ 90 mmHg and decrease from baseline ≥ 20 mmHg
High and increase from baseline	≥ 160 mmHg and increase from baseline ≥ 20 mmHg	Birth/0 to 27 days old : ≥ 85 mmHg and increase from baseline ≥ 20 mmHg 28 days/1 month to 23 months old: ≥ 98 mmHg and increase from baseline ≥ 20 mmHg 24 months/2 years to <6 years old: ≥ 101 mmHg and increase from baseline ≥ 20 mmHg 6 to <12 years old : ≥ 108 mmHg and increase from baseline ≥ 20 mmHg 12 to 16/18 years old : ≥ 119 mmHg and increase from baseline ≥ 20 mmHg
Diastolic blood pressure supine		
Low and decrease from baseline	≤ 45 mmHg and decrease from baseline ≥ 10 mmHg	Birth/0 to <6 years old : ≤ 34 mmHg and decrease from baseline ≥ 10 mmHg 6 to <12 years old : ≤ 48 mmHg and decrease from baseline ≥ 10 mmHg 12 to 16/18 years old : ≤ 54 mmHg and decrease from baseline ≥ 10 mmHg
High and increase from baseline	≥ 110 mmHg and increase from baseline ≥ 10 mmHg	Birth/0 to 27 days old : ≥ 50 mmHg and increase from baseline ≥ 10 mmHg 28 days/1 month to 23 months old: ≥ 54 mmHg and increase from baseline ≥ 10 mmHg 24 months/2 years to <6 years old: ≥ 59 mmHg and increase from baseline ≥ 10 mmHg 6 to <12 years old : ≥ 72 mmHg and increase from baseline ≥ 10 mmHg 12 to 16/18 years old : ≥ 78 mmHg and increase from baseline ≥ 10 mmHg
Heart rate supine (adults)		
Low and decrease from baseline	≤ 50 bpm and decrease from baseline ≥ 20 bpm	
High and increase from baseline	≥ 120 bpm and increase from baseline ≥ 20 bpm	

References:

- for adults: Criteria for Potentially Significant Abnormalities – for Phase 2/3 studies (oncology excepted) - Version 3.0 - 21-MAY-2014
- for children: Criteria for Potentially Clinically Significant Abnormalities for Studies in Children - Version 3.0 - 21-MAY-2014

Summary of statistical analyses

EFFICACY ANALYSIS

Endpoint	Analysis population	Primary analysis	Supportive analysis	Subgroup analysis	Other analyses
PCR-corrected ACPR at Day 28	PP	Logistic regression on exposure-response with odds ratio estimates, 2-sided 95% Wald CI and p-value	No	No	Proportion, percentage, 2-sided exact binomial 95% CI by treatment group
PCR crude ACPR at Day 28	PP	Logistic regression on exposure-response (resp. dose-response) with odds ratio estimates, 2-sided 95% Wald CI and p-value	No	No	Proportion, percentage, 2-sided exact binomial 95% CI by treatment group
PCR-corrected ACPR at Day 28	PP	Logistic regression on dose-response vs odds ratio estimates, 2-sided 95% Wald CI and p-value	No	No	Proportion, percentage, 2-sided exact binomial 95% CI by treatment group
Parasite Reduction Rate at 24, 48 h, and 72 h	PP	Descriptive statistics by treatment group and time of measurement.	No	No	No
Parasitemia data as a continuous endpoint	PP	Descriptive statistics by visit and treatment group. Time profile plots by treatment group	No	No	No
Parasite clearance rate	PP	Descriptive statistics by visit and treatment group.	No	No	No
Time to parasite Clearance, to fever clearance, 50% and 99% parasite reduction, recrudescence or re-infection, elapsed below LOQ of parasitemia.	PP	Kaplan Meier estimator and Cox model	No	No	No

SAFETY ANALYSES

Endpoint	Analysis population	Primary analysis	Supportive analysis	Subgroup analysis	Other analyses
Adverse Events, clinical laboratory data, ECG, vital signs, LFT, Physical examination	Safety	Follow safety guidelines	No	No	No

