1.6 STATISTICAL MODIFICATIONS MADE IN THE STATISTICAL ANALYSIS PLAN

The primary efficacy population will be the PK/PD population instead of the mITT population stated in the protocol.

A per-protocol [PP] population was added in order to align the analysis population with the primary endpoint of the study. All populations have been further clarified from the protocol definitions

The derivation of the secondary endpoint, Fever clearance time (FCT), has been added. FCT will be assessed by measuring the time from the first dose until the first time that the body temperature dropped and remained <37.5 °C.

Time to 50% parasite reduction (T_{PC50}) will also be calculated in addition to the time to 99% PR.

The evaluation of the relationship between parasitemia (as measured on thick blood film and/or by qPCR) and concentration of OZ439/FQ may be performed in a separate analysis pooling data from different studies and be reported in a separate report.

The terminal half-life ($t_{1/2}$) for OZ439 and ferroquine will not be estimated as this endpoint does not contribute to the objectives of the study.

The definition of baseline to be used for efficacy analyses has been clarified.

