2.1.4.1 Primary efficacy endpoint

The primary efficacy endpoint is the PCR-corrected ACPR at Day 28. The PCR-corrected ACPR at Day 28 will be derived from the efficacy evaluation at Day 28 defined as follows:

Efficacy evaluation at Day 28	Per Protocol	miITT
	PCR-corrected ACPR at Day 28	PCR-corrected ACPR at Day 28
ACPR	Success	Success
ETF	Failure	Failure
LCF before Day 7	Failure	Failure
LCF on or after Day 7 or LPF		
- P. falciparum recrudescence	Failure	Failure
- P. falciparum reinfection prior to Day 28	Excluded from analysis	Failure
- P. falciparum reinfection on Day 28	Success	Success
- Other species mixed with P. falciparum recrudescence	Failure	Failure
- Other species mixed with P. falciparum reinfection	Excluded from analysis	Failure
- Undetermined, negative or missing PCR	Excluded from analysis	Failure
Rescue therapy start without previous ETF, LCF, LPF, or other species infections, and not classified as a protocol violation	Before Day 7: Failure On/after Day 7: excluded from analysis	Failure
Other species infection without P. falciparum reemergence	Excluded from analysis	Failure
Lost to follow-up	Excluded from analysis	Failure
Withdrawal*	Excluded from analysis	Failure
Protocol violation**	Excluded from analysis	Failure

(*): Patient's request - Investigator's judgement - Adverse event - Other

(**): protocol violations potentially impacting efficacy assessment at Day 28 for the PP population as defined in [Section 2.3.2.2](#)

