2.3 ANALYSIS POPULATIONS

Patients treated without being randomized will not be considered randomized and will not be included in the PK/PD efficacy population.

For any patient randomized more than once, only the data associated with the first randomization will be used in any analysis population.

The primary analysis of the study will be performed using the PKPD efficacy population (see section 2.3.5).

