2.3.5.1 PK/PD efficacy population

The PK/PD efficacy population will be the primary efficacy population.

Pharmacokinetic/pharmacodynamics (PK/PD efficacy) population will include those patients in both the PK and mITT populations with additional criteria specified below,..

Patients need at least one evaluable blood sample for PK of both OZ439 and FQ.

Parasitemia data for patients with rescue treatment started before the considered time point will be excluded from this time point until Day 28.

In case of vomiting or other reasons interrupting the administration of the complete dose, and if valid parasitemia data post-randomization available, then patients will be included in the PK/PD efficacy population.

As defined in [Section 2.1.4.1](#), there are certain criteria that would exclude patients from having an evaluable PCR-corrected ACPR at Day 28::

- Other species infection without *P. falciparum* reemergence
- Lost to follow-up,
- Withdrawal,
- Protocol violation.

Protocol violations considered above are those potentially impacting efficacy assessments at Day 28:

- Patients who needed rescue treatment because they did not take IMP or due to vomiting during IMP administration.
- Patient presenting severe malaria or receiving a rescue treatment due to severe malaria during the first 24 hours following IMP start (i.e. wrong inclusion).
- Start of rescue therapy before Day 28 assessment not due to: vomiting during IMP administration, wrong inclusion, treatment failure (per investigator or per WHO criteria), or other species infections.
- Missing baseline parasitemia, and positive parasitemia at 48 or 72 hours.
- Intermittent missing or out of window post-baseline parasitemia preventing to evaluate ACPR Day 28.
- Missing post-baseline body temperature preventing to evaluate ACPR Day 28.
- Out of Day 28 time window parasitemia preventing to evaluate ACPR Day 28.
- Patients with at least one enrolment violation among the following:
 - Patients who meet exclusion criteria E 01 which is: “Presence of severe malaria (according to WHO definition)”.
 - Patients violator for inclusion criteria I02 which is: “Presence of *P. falciparum* malaria, with a fever as defined with axillary temperature ≥ 37.5 degree Celsius ($^{\circ}\text{C}$) or oral/

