2.4.4.2 Analyses of secondary efficacy endpoints

Apart from Day 28 crude ACPR, all other secondary efficacy endpoints will be reported and analysed on the mITT only.

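### The SAP's summary table puts the primary analysis on the PP population against the body text, and the endpoint coding table has no column for the designated PK/PD efficacy population

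*SAP*

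**What the plan says.** **Population, body of the SAP.** Section 1.6 declares the change from the protocol: "The primary efficacy population will be the PK/PD population instead of the mITT population stated in the protocol". Section 2.3 repeats it ("The primary analysis of the study will be performed using the PKPD efficacy population"), as does 2.3.5.1 ("The PK/PD efficacy population will be the primary efficacy population"). Sections 2.2 and 2.4.4 agree. Section 2.4.4 puts the secondary analyses on mITT unless otherwise stated. Section 2.4.4.2 says that, apart from crude ACPR, "all other secondary efficacy endpoints will be reported and analysed on the mITT only". Section 2.4.4.1.2 describes PCR-corrected ACPR in both PP and mITT.

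**Population, summary table.** The table of statistical analyses at the end of Appendix B gives PP as the population for the primary row ("Logistic regression on exposure-response with odds ratio estimates, 2-sided 95% Wald CI and p-value") and for every other efficacy row.

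**Role of PP.** Section 1.6 adds: "A per-protocol [PP] population was added in order to align the analysis population with the primary endpoint of the study".

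**Coding.** The table in 2.1.4.1 derives PCR-corrected ACPR in two columns, PP and mITT. In the row for *P. falciparum* "reinfection prior to Day 28", PP excludes the patient and mITT records a failure. There is no PK/PD efficacy column. Section 2.3.5.1 builds that population from patients who are in both the PK and mITT populations, then adds further criteria.

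**The concern.** The primary test is a Wald test on a binary response, so two things must be fixed in advance: who enters the model, and what value each patient carries. The body settles the population, and the summary table contradicts it. The value carried by some patients is not settled in writing. A programmer who follows the construction of the PK/PD efficacy population from mITT could apply the mITT column. One who follows the endpoint definition in 2.1.4 would exclude the same patients.

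The difference matters because a re-infection says nothing about whether the drug cleared the original parasites. Scored as failures, re-infections add events unrelated to OZ439 exposure, and they fall mostly in the high-exposure arms, where most patients are successes.

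**Working it through.** **1. Where the two coding columns differ (SAP 2.1.4.1), and what 2.3.5.1 says**

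| Category | PP | mITT | Listed as not evaluable in 2.3.5.1? |
|---|---|---|---|
| Other species without *P. falciparum* re-emergence | Excluded | Failure | Yes |
| Lost to follow-up | Excluded | Failure | Yes |
| Withdrawal | Excluded | Failure | Yes |
| Protocol violation | Excluded | Failure | Yes |
| *P. falciparum* re-infection before Day 28 | Excluded | Failure | No |
| Other species mixed with re-infection | Excluded | Failure | No |
| Undetermined, negative or missing PCR | Excluded | Failure | No |
| Rescue on or after Day 7 without WHO criteria, not a violation | Excluded | Failure | No |

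The first four rows are settled as exclusions, which is the PP convention. The last four are not assigned. *P. falciparum* re-infection on Day 28 itself is a success in both columns, so only earlier re-infections are at issue.

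**2. The plan's own power.** Inputs from Protocol Appendix 8 (also SAP 1.3):
- logit(p) = 3.23 + 0.12·FQ + 0.73·OZ439 − 1.27·log10(baseline parasitemia)
- log10 parasitemia normal (mean 4, SD 0.55), truncated to 3.48–5.5
- arm rates 72%, 81%, 91% and 97%; 30 evaluable per arm; two-sided 5% Wald test on the OZ439 coefficient

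The exposure distributions are not given. I assumed log-normal exposures, with medians calibrated to the four rates, FQ CV 30–80%, OZ439 CV 40–130% and correlation 0.2. Simulated power was 88.7–93.0%, which agrees with the stated figure of around 90%.

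**3. Effect of the coding on arm rates.** Let r be the assumed chance of re-infection before Day 28 among patients who would otherwise succeed, equal across arms.
- Failure coding: p becomes p(1−r). At r = 10% the arms are 64.8%, 72.9%, 81.9% and 87.3%.
- Exclusion: p becomes p(1−r)/(1−pr). At r = 10% they are 69.8%, 79.3%, 90.1% and 96.7%.

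Odds ratio, 1000 mg against FQ alone:
- Planned: (0.97/0.03)/(0.72/0.28) = 12.6
- Exclusion: each arm's odds are multiplied by (1−r), so the ratio stays at 12.6
- Failure, r = 2%: (0.9506/0.0494)/(0.7056/0.2944) = 8.0
- Failure, r = 5%: (0.9215/0.0785)/(0.684/0.316) = 5.4
- Failure, r = 10%: (0.873/0.127)/(0.648/0.352) = 3.7

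Few patients are needed. Expected successes are 30 × (0.72+0.81+0.91+0.97) = 102.3, so r = 2%, 5% and 10% correspond to about 2, 5 and 10 patients.

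**4. Effect on power** (FQ CV 50%; OZ439 CV 60 / 80 / 100%)

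| Assumed r | Excluded (PP coding) | Failure (mITT coding) |
|---|---|---|
| 2% | 93.0 / 92.6 / 89.6% | 82.2 / 78.3 / 73.4% |
| 5% | 93.0 / 92.0 / 89.6% | 66.3 / 60.8 / 58.6% |
| 10% | 92.7 / 91.8 / 90.2% | 50.4 / 43.7 / 39.6% |

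With FQ CV 40% and OZ439 CV 60%, failure coding gave 70% at r = 5% and 54% at r = 10%. Across all runs the ranges are about 88–94% for exclusion and, for failure coding, 73–84%, 58–71% and 39–54% at r = 2%, 5% and 10%.

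**5. Membership of the designated population.** Section 2.3.5.1 requires an evaluable PK sample for both OZ439 and FQ. The flow chart in SAP Appendix A says OZ439 is not measured in Arm A. Read literally, the FQ-alone arm has no members in the primary population.

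**The case against.** The strongest reply is that nothing of substance is open. Most of it stands.

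- **Population.** Five places in the body name PK/PD efficacy, one of them as a declared change from the protocol. The summary table is out of step elsewhere too. It lists Kaplan-Meier and Cox for 50% and 99% parasite reduction, where 2.4.4.2.5 specifies a linear model. It reads as an unreconciled summary. A reader might infer two rival primary populations, or take the sentence in 1.6 on adding PP as making PP primary. The documents do not support this: the same section names PK/PD, and PP has its own use in 2.4.4.1.2.
- **Coding.** A reader might infer that a subset of mITT inherits mITT scoring. The text leans the other way. SAP 2.1.4 calls re-infected patients non-evaluable for the PCR-corrected endpoint, and Protocol 10.3.1.1 says a confirmed new infection is not a treatment failure. Section 2.3.5.1 treats as not evaluable four categories that only the PP column excludes. Section 2.4.4.1.1 excludes, rather than fails, patients whose missing Day 28 parasitemia cannot be imputed. The absence of re-infection from the list in 2.3.5.1 proves little, since the PP section has the same four bullets.
- **Size.** Protocol 5.4 aims at settings with low re-infection risk.

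What remains: the PP section carries a note that new infections are non-evaluable, and the near-parallel PK/PD section lacks it. The mITT column contradicts the general definition, so that definition is not applied uniformly. Nothing outside the table covers undetermined PCR or late rescue.

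**Conclusion.** The inconsistency is real and touches the primary response variable, but it is a reconciliation error and not an open choice of primary analysis. The summary table is wrong against the body in the primary row and in the rows the body assigns to mITT only. For four outcome categories the coding in the PK/PD efficacy population is implied, not stated; the implied coding is PP, and the wrong column would be costly. Exclusion holds power at about 88–94%. Failure coding would cut it to about 73–84% at 2% re-infection, 58–71% at 5% and 39–54% at 10%.

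These figures rest on assumed exposure CVs and on assumed re-infection rates equal across arms. They show what a misapplied column would cost and do not forecast this trial's power. A reader might also infer that the coding will be picked after the data are seen. The documents do not show that; they show only that the rule is not written where the analyst will look for it.

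**What to change.** In the SAP, before database lock:

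1. Correct the summary table to PK/PD efficacy for the primary exposure-response model and to the populations in 2.4.4 to 2.4.4.2 for the other rows.
2. Add a PK/PD efficacy column to the table in 2.1.4.1, using the PP coding for every category where the present columns differ. This includes mixed-species re-infection, undetermined, negative or missing PCR, and late rescue.
3. Repeat in 2.3.5.1 the note from 2.3.2.2 that new infections are non-evaluable for PCR-corrected ACPR.
4. State in 1.6 that PP is not the primary population and say what it is used for.
5. Reword 2.3.5.1 so that the OZ439 PK sample requirement does not apply to Arm A.

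The cost is SAP wording only. No data collection, sample size or protocol procedure changes.
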